7.5.5 Urine Pregnancy Test

An in-office, highly sensitive urine pregnancy test must be performed for all female subjects of child-bearing potential at Screening and the Week 12 Visit (Early Termination, or Final Visit). All female subjects of childbearing potential must have a negative urine pregnancy test prior to randomization. Urine pregnancy testing should also be conducted at an unscheduled visit for any female who is suspected of being pregnant. Any female who becomes pregnant should be withdrawn from the study and followed to term. The CRO/Sponsor must be notified of any pregnancy that occurs while on

CONFIDENTIAL

Version Date: 10 July 2015

therapy. In the event of pregnancy, the site will complete a pregnancy report form to capture the pregnancy outcome.

7.5.6 Adverse Event

7.5.6.1 Definition of Adverse Event

An adverse event (AE) is any unfavorable and unintended sign (including a clinically significant abnormal laboratory finding, for example), symptom, or disease temporally associated with the use of a medicinal product, whether or not considered related to the medicinal product. Clinical signs and symptoms of rosacea: erythema, telangiectasia, burning, dryness, scaling/peeling and pruritus are considered as part of the baseline dermatological history. If a new rosacea sign or symptom or worsening of a rosacea sign or symptom is believed by the investigator to be related to the study drug and not the disease, then it should also be recorded as an AE.

At each visit, the study site personnel will question the subject about adverse events using an open question taking care not to influence the subject's answers, e.g., "Have you had any problems since your last visit?"

Any adverse event, whether or not it is related to the test products, will be reported on the source document and eCRF along with the date of onset, the severity, the relationship to the test product and the outcome. Under certain circumstances, additional information may be requested.

When an adverse event persists at the end of the study, the Investigator will ensure a follow-up of the subject until the Investigator/CRO/Sponsor agree that the event is satisfactorily resolved or that no further follow-up is required.

7.5.6.2 Severity and Relationship of Adverse Event to Study Drug

The severity of an adverse event is to be scored according to the following scale:

1	Mild	Awareness of sign or symptom, but easily tolerated
2	Moderate	Moderate Discomfort enough to cause interference with usual activity
3	Severe	Severe Incapacitation with inability to work or perform usual activity

The relationship of an adverse event to study drug is to be assessed according to the following definitions:

- Not related – no temporal association or the cause of the event has been identified, or the drug cannot be implicated based upon available information.
- Possibly Related – temporal association, but other etiologies are likely to be the cause. However, involvement of the drug cannot be excluded, based upon available information.

CONFIDENTIAL

Version Date: 10 July 2015

- Definitely Related – established temporal or other association (e.g., re-challenge) and event is not reasonably explained by the subject's known clinical state or any other factor, based on available information.

7.5.7 Serious Adverse Event:

A serious adverse drug event (SAE) is any adverse event (AE) or suspected adverse reaction (SAR) that, in the view of either the investigator or sponsor, results in any of the following outcomes:

- death;
- a life-threatening adverse event or life-threatening suspected adverse reaction, (the term "life-threatening" in the definition of "serious" refers to an event or suspected adverse reaction in which in the view of either the investigator or sponsor, its occurrence places the patient or subject at immediate risk of death. It does not include an adverse event or suspected adverse reaction that, had it occurred in a more severe form, might have caused death);
- inpatient hospitalization or prolongation of existing hospitalization;
- Persistent or significant incapacity; or substantial disruption of the ability to conduct normal life functions; or
- A congenital anomaly/birth defect.

Important medical events that may not result in death, be life-threatening, or require hospitalization may be considered a serious adverse drug experience when, based upon appropriate medical judgment, they may jeopardize the patient or subject and may require medical or surgical intervention to prevent one of the outcomes listed in the serious definition above. Examples of such medical events include allergic bronchospasm requiring intensive treatment in an emergency room or at home, blood dyscrasias or convulsions that do not result in inpatient hospitalization, or the development of drug dependency or drug abuse.

The Investigator or designee must report any SAE occurring in a subject receiving study medication to the Medical Monitor immediately (within 24 hours (1 business day) of becoming aware of the event), even if the SAE does not appear to be drug-related. This should be done by telephone and by sending a copy of the Serious Adverse Event form (via fax or email pdf copy) plus other supporting documentation, as required.

All additional follow-up evaluations must also be reported as soon as possible. All SAEs will be followed until the CRO/Sponsor agrees that the event is satisfactorily resolved or that no further follow-up is required.

The CRO/Sponsor will be responsible for notifying the relevant authorities of any SAE according to applicable regulations. The CRO/Sponsor will also ensure that any central IRB/IEC and any other participating Investigators are notified of the SAE. The PI is responsible for ensuring that their local IRB/IEC, if applicable, is notified of the SAE, as per the IRB/IEC standard operating procedures.

Serious Adverse Events must be reported immediately to the appropriate medical monitor as listed below:

CONFIDENTIAL

Version Date: 10 July 2015

Medical Monitors:

[REDACTED]

[REDACTED]

[REDACTED]

[REDACTED]

7.6 TEST MATERIALS**7.6.1 Administration**

Study drug will be applied by the subject to the entire area of the face, once daily, in the morning, for a period of 12 weeks after performing the first application of study drug at the study site, under the supervision of the study coordinator or designee to ensure the subject understands the treatment application instructions (see Appendix A, Instructions on Application of Study Drug). The subject will be provided a copy of the Instructions on Application of Study Drug. Once the subject has read the instructions and demonstrated proficiency in application at the study site, subjects will continue daily treatment application, each morning, during the treatment period, in an outpatient setting.

Subjects will be instructed to wash their face with a non-medicated soap or soapless cleanser at least 15 minutes prior to application of the study drug. The study drug is packaged in a tube. The cap of the tube should be removed and a thin film coating of the gel should be applied to the entire face, avoiding contact with the eyes, mouth and inside the nose. The dose applied will be applied as a thin film, approximately 0.4 gram each day preferably in the morning.

At the Baseline visit and Week 3, 6 and 9 visits only subjects will be dispensed one tube of study gel. Each tube contains enough gel for 4 weeks of treatment. When the tube is dispensed and prior to application of study drug, the tube will be dated and weighed and the weight will be recorded in the source documents and eCRF. When the used tubes are returned at the next visit, the tube will be weighed again, and the weight will be recorded in the source documents and the eCRF. At each visit, the subject's diary should be reviewed to determine if they missed any applications since the last visit. Reported missed applications should be recorded in the eCRF. In addition, the date of the last application should be collected. At each visit the returned tube will be weighed to assess product use. If necessary, the subject will be re-instructed on study drug application if compliance is an issue. All tube weighing will be done with the cap in place.

CONFIDENTIAL

Version Date: 10 July 2015

study drug inside the kit. Treatment kits will be shipped to the study sites when IRB/IEC approval has been obtained and all required study documents are submitted to the sponsor.

Once it has been established that subjects are eligible to participate in this study, each eligible subject will be assigned a treatment kit from those available at the site, which is labeled with the assigned kit number. Treatment kits must be assigned to subjects using the Interactive Web Response System (IWRS).

7.6.4 Unblinding a Subject

This is a double-blind, multicenter study. Subjects will be randomized to once daily treatment with either omiganan topical gel or vehicle. Study drug supplies will be packaged in a manner supporting the blinding of the study.

Unblinding a subject, if needed, will be done through the IWRS. Unblinding a subject's treatment assignment should ONLY be performed in an emergency, when knowing the identity of a subject's assigned treatment is essential to their continuing medical care. If at all possible, every attempt should be made to contact the Medical Monitor to discuss this before opening the blinded panel to determine the subject's treatment assignment. The contact information for the Medical Monitor's is provided on the front page of the protocol. In the event of unblinding, the Medical Monitor and Project Manager must be notified immediately (within 24 hours(1 business day)), and the circumstances under which the code for a given subject was broken must be documented in the subject's eCRF.

7.6.5 Packaging

Study drug will be provided in 20-gram tubes. Drug supplies will be packaged to provide one treatment kit that contains 5 tubes of study drug per subject. Four tubes will be provided in order to dispense a tube at Baseline, Weeks 3, 6 and 9; 1 extra tube will be in the kit in case tubes are lost or damaged. Each tube will be printed with the treatment kit number that will correlate through the randomization list to the contents of the tube.

7.6.6 Labeling

The requirements for drug product labeling will comply with the Regulations of the country where the clinical trial will be conducted.

Subjects will be provided a leaflet or card to keep with them at all times during the study that will provide the investigational site with the address and telephone number of the main contact for information on the product, clinical trial and for emergency unblinding.

Each treatment kit (consisting of 5 tubes of study drug) will be labeled with language that adheres to the applicable regulatory requirements in each country.

Each tube within the treatment kit will be labeled with labeling that corresponds to the treatment kit number. The study site personnel will write in the subject number and date of dispensing on the label

CONFIDENTIAL

Version Date: 10 July 2015

when dispensing a tube. Tube labeling will contain language that adheres to the applicable regulatory requirements in each country.

7.6.7 Subject Dosing and Use Instructions

Under the supervision of the study coordinator or designee, the first dose of study drug will be applied by the subject, as a means of educating subjects in the proper technique for applying the study drug (see Appendix A for instruction on applying the drug). Once the subject has shown proficiency in application, subjects will then apply the dose each day in the morning, in an outpatient setting.

7.6.8 Treatment Compliance

Subjects should not miss ANY visits to the study site for status assessments. Study drug treatment compliance will be assessed by reviewing the diary for any missed applications since the last visit or based on subject reported information on missed applications in the event of a lost diary. Subjects should be applying the topical gel each day during the study treatment period.

7.6.9 Dispensing and Return of Study Product

For use in the outpatient setting, 1 tube of study drug will be dispensed to each subject from their assigned study drug supply kit at Baseline, and again at their Week 3, 6 and 9 visits. The first dose of study drug will be applied at the study site. Subjects will be instructed on the proper procedure for study drug application for subsequent doses.

When a new tube of study drug is dispensed, study personnel must record the date dispensed and subject number on the label. The dispensing information must be recorded in the source documents.

The tube should be weighed prior to dispensing to the subject and again after the subject returns the tube to the clinical study site. The weight of the tube should be recorded to the nearest tenth of a gram. Tubes should be weighed with the cap on.

The subject will be instructed to return the tube of study drug at each study visit (Weeks 1, 3, 6, 9, and 12) to check compliance. At the Week 3, 6 and 9 Visit, the used tube will be exchanged for a new tube of study drug. One extra tube is available in each kit for dispensing in the event that tubes are lost or damaged.

7.6.10 Accountability

In accordance with local country regulations, the Investigator must agree to keep all clinical supplies in a secure location with restricted access.

Upon receipt of the clinical supplies, the Investigator or designee will conduct a complete inventory of all test materials and assume responsibility for storage and dispensing. Dispensation and return of test material must be appropriately documented. Under no circumstance should any of the clinical supplies sent to the Investigator be used in any unauthorized manner.

CONFIDENTIAL

Version Date: 10 July 2015

All used and unused clinical supplies will be appropriately inventoried and returned to the designated facility as specified by the Sponsor.

7.6.11 Prior and Concomitant Medication/Therapy

Therapies used within one month prior to the Baseline visit should be recorded on the Previous/Concomitant Medication/Therapy Form of the CRF. Washout medications should be listed on the Previous/Concomitant Medication/Therapy Form, when applicable. Rosacea treatments used in the last 5 years should be recorded.

Any therapy used by the subject either at or following the Baseline visit through study completion will be considered concomitant therapy; e.g., aspirin, Tylenol, birth control pills, vitamins, etc. Every attempt should be made to keep concomitant therapy dosing constant during the study. Any change to concomitant therapy should be noted on the Previous/Concomitant Therapy page in the eCRF.

An Adverse Event should be recorded for any subject starting a concomitant therapy (except therapies used as prophylaxis) to treat any health condition/event not identified in the subject's medical history.

Subjects should wash their face 15 minutes prior to study drug applications. Subjects must adhere to the following restrictions during the treatment period starting in the morning of Day 1:

- Showering/bathing (when subject showers/bathes, he or she should wait at least 15 minutes prior to applying study drug).
- Males should shave at the same time every day, at least 15 minutes before study drug application.
- Wait until the gel dries before applying makeup.
- Refrain from sunbathing, using sun tanning booths/beds, or excessive exposure to the sun. No new lotions, gels, powders, moisturizers, etc., are to be used on the skin in the treatment areas. A bland moisturizer may be used throughout the study. All makeup, approved lotions, moisturizers, etc. and sunscreen should be applied after the study gel is dry.

7.6.11.1 Excluded Concomitant Therapy

No other rosacea treatment, other than the study drug, will be permitted. Receiving interfering rosacea therapy during the study will be deemed a major protocol violation and may exclude the subject from the per protocol population for efficacy analyses. The medical monitor should be notified of deviations related to concomitant therapy. Interfering concomitant therapies include those listed below:

Interfering Topical Therapies (on the face)

- Abradants, astringents, toners, facials, masks, washes, or medicated facial cleansers
- Tanning booths/sunbathing, excessive exposure to the sun (tanning is not permitted)
- Antibiotics other than topical ocular application
- Antimicrobial soaps
- Corticosteroids

CONFIDENTIAL

Version Date: 10 July 2015

- Other anti-inflammatory drugs
- Retinoids
- Other acne or rosacea treatments (e.g., benzoyl peroxide, alphahydroxy acids, salicylic acid, azelaic acid, or metronidazole)

Interfering Systemic Therapies

- Antibiotics
- Corticosteroids other than inhaled/nasal corticosteroids
- Other acne or rosacea treatments (including oral retinoids or therapeutic vitamin A supplements)
- Change in dose, initiation and/or discontinuation of estrogen therapy (e.g., Gynogen, Valergen, Depo-Testadiol, Depogen, birth control pills)

7.7 STATISTICAL METHODS PLANNED

7.7.1 General Considerations

Unless otherwise specified, all statistical tests will be two-sided with a significance level of 0.05.

7.7.2 Sample Size Determination

The primary objective of the study is to show superiority of Omiganan over vehicle for the treatment of rosacea in patients with severe papulopustular rosacea (IGA grade 4 with baseline inflammatory lesion count of ≥ 30). A sample size calculation was made for two co-primary endpoints. For change from baseline in inflammatory lesions, it is assumed that in the omiganan treatment arm, subjects will have an average reduction of 13.5 inflammatory lesions, compared to 4 in the vehicle arm. The standard deviation is assumed to be 12. For 95% power, a sample size of 86 subjects (43 per group) is needed. For Investigator Global Assessment (IGA), it is assumed that Clear or Almost clear (IGA of 0 or 1) at Week 12 has a lesser power than a 2 grade (point) reduction. It is also assumed that 17% of the subjects in the Omiganan treatment arm versus 6% in the vehicle arm will have an IGA of Clear or Almost Clear at Week 12. For 95% power and using a Fisher's Exact test, 450 subjects (225 in each arm) are needed. Therefore, the number of subjects needed to ensure at least 95% power for both endpoints is 450.

The sample sizes were calculated using 95% power in order to ensure 90% power across two Phase 3 studies.

7.7.3 Randomization

Subjects providing written informed consent and having met all inclusion and exclusion criteria will be randomized to 1 of 2 treatment groups in a 1:1 ratio, according to a predetermined computer-generated randomization code.

CONFIDENTIAL

Version Date: 10 July 2015

Subjects will be randomized to treatment using an Interactive Web Response System (IWRS). The randomization scheme will include investigative site. The randomization will be performed using permuted blocks.

7.7.4 Analysis Populations

The 'Intent-to-treat' (ITT) analysis population will include all randomized subjects. The ITT population will be the primary population for all efficacy analyses.

The "All-treated" analysis population will consist of all subjects receiving at least one application of study medication. All safety analyses will be performed on the all-treated population.

The Per-Protocol (PP) population will include all subjects in the ITT population who provide Baseline and Week 12 efficacy data for all primary endpoints and complete the 12-week treatment period without any major deviations from the protocol.

The subjects to be included in the PP analysis population will be determined by the Sponsor/CRO prior to the unblinding of the study. The PP population will be secondary for the co-primary endpoints only.

7.7.5 Handling of Missing Data

The primary method of dealing with missing data is multiple imputation (MI) technique. All co-primary and secondary endpoints will be analyzed using MI for missing data. As a sensitivity analysis, Observed case and Baseline Observation Carried Forward (BOCF) will be utilized for the co-primary endpoints only.

In general, data will not be imputed for safety analysis.

7.7.6 Efficacy Endpoints

7.7.6.1 Co-primary Endpoints

- The absolute change from Baseline to Week 12 in inflammatory lesions.
- IGA at Week 12: 2 grade reduction; Clear or almost Clear (IGA 0, or 1)

7.7.6.2 Secondary Endpoints

- The absolute change from baseline to Week 9 in inflammatory lesions (papules and pustules).
- The absolute change from baseline to Week 6 in inflammatory lesions (papules and pustules).
- IGA at Week 9: 2 point reduction; Clear or Almost Clear (IGA 0, 1).
- IGA at Week 6: 2 point reduction; Clear or Almost Clear (IGA 0, 1).

CONFIDENTIAL

Version Date: 10 July 2015

7.7.6.3 Exploratory Endpoints

- The absolute change from baseline to Weeks 1 and 3 in inflammatory lesions (papules and pustules).
- Percentage of subjects with an IGA of clear or almost clear (0 or 1) at Weeks 1 and 3.
- Percentage of subjects with a 2 point IGA reduction at Weeks 1 and 3.
- Percentage of subjects with an Investigator's Assessment of Erythema (IAE) of clear or almost clear (0 or 1) at each visit.
- Percentage of subjects with telangiectasia score of none or mild (0 or 1) at each visit.
- Percentage of subjects with scaling/peeling score of none or mild (0 or 1) at each visit.
- Percentage of subjects with pruritus score of none or mild (0 or 1) at each visit.

7.7.7 Demographic and Baseline Characteristics

Continuous demographic and baseline parameters will be summarized by the number of non-missing observations, mean, standard deviation, median, minimum, and maximum. Categorical parameters will be summarized by frequencies and percentages.

7.7.8 Subject Disposition

Study completion status and reasons for discontinuation will be summarized by frequencies and percentages.

7.7.9 Study Product Exposure

The number of days of exposure will be summarized by the number of non-missing observations, mean, standard deviation, median, minimum, and maximum.

7.7.10 Efficacy Analysis

The co-primary endpoint of absolute change from baseline in inflammatory lesions will be analyzed using an Analysis of Covariance (ANCOVA) model, with treatment as a main effect, and center as a covariate. To investigate consistency of efficacy results across study centers, treatment by study center interaction will be tested at 0.10 level of significance, and if significant, it will be further explored.

The co-primary endpoint of IGA will be tested in the following manner: the 2 grade reduction, and the Clear or Almost Clear (0, 1) will be tested using the Hochberg procedure as follows: Statistical significance will be concluded if both endpoints are significant at a two-sided 0.05 level, or either endpoint is significant at a two-sided 0.025 level. Both IGA endpoints will be analyzed using a Cochran–Mantel–Haenszel (CMH) test, with center as the stratification factor. If the overall IGA response rates are less than 10%, a Fisher's Exact test may be used to corroborate the CMH test. All tests of the co-primary endpoints will be analyzed.

CONFIDENTIAL

Version Date: 10 July 2015

If the co-primary endpoints of absolute lesion reduction and the two IGA endpoints (2 grade reduction, and Clear or Almost Clear (0, 1)) are both significant, the secondary endpoints will be analyzed sequentially in the order listed as follows:

- Test first secondary endpoint at 0.05. If not significant, stop; otherwise,
- Test second secondary endpoint at 0.05. If not significant, stop; otherwise,
- Test third secondary endpoint at 0.05 using Hochberg (similar to the primary method). If not both IGA (0,1) and IGA 2 point reduction are significant, stop; otherwise,
- Test fourth secondary endpoint at 0.05 using the Hochberg method.

For all efficacy analyses, small centers may be pooled in order to ensure sufficient cell counts for statistical testing.

Subgroup analyses (e.g. Gender, Age, Race, and Center) of the co-primary endpoints will be performed.

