7.2 SELECTION OF STUDY POPULATION

7.2.1 Inclusion Criteria

Subjects must meet each of the following criteria to be considered eligible for entry into the study:

1. Subjects who provided written informed consent to participate in the study.
2. Healthy, male and non-pregnant female subjects, 18 years of age or older.
3. A diagnosis of papulopustular rosacea with ≥ 30 inflammatory facial lesions (papules, pustules) at Baseline. Subjects must have no more than 2 nodular lesions, at Baseline.
4. Subjects with the presence of telangiectasia at Baseline.
5. Subjects with an erythema score of at least 2 on the Investigator Assessment of Erythema (IAE) scale at Baseline.
6. Subjects with a grade 4 (severe rosacea) on the 5-point Investigators Global Assessment (IGA) scale at Baseline.
7. Non-nursing, female subjects of child bearing potential, who are using a highly effective form of birth control or females not of childbearing potential due to menopause (must be postmenopausal for at least one year).
 - Highly effective methods of birth control are defined as those, alone or in combination, that result in a low failure rate (i.e. less than 1% per year) when used consistently and correctly. Forms of birth control include: Oral (birth control pills), Intravaginal: (e.g. NuvaRing®), Implantable (e.g. Norplant®), injectable (e.g. Depo-Provera®) or transdermal (e.g. Ortho Evra®) contraception; intrauterine device (IUD); double-barrier (diaphragm or condom with spermicidal gel or foam); for two months prior to study enrollment (see exclusion criteria #6) or a vasectomized partner or true abstinence (in line with preferred and usual lifestyle of subject) with an acceptable form of birth control should the subject become sexually active. Periodic abstinence (e.g., calendar, ovulation, symptothermal, post-ovulation methods) and withdrawal are not acceptable methods of contraception. All female subjects of child bearing potential must undergo an in-office, highly sensitive urine pregnancy test, with a negative result, prior to being randomized to receive study drug. In addition, women of childbearing potential must agree to have a highly sensitive urine pregnancy test at the end of the study.
8. Subjects who have used the same brand of soap, make-up, hair products, or shaving lotion/foam/cream/gel for a period of at least four weeks prior to the Baseline Visit and agree not to change these product brand/types during the study.

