7.4.1 Investigators Global Assessment (IGA)

The IGA should be performed at screening and each study visit (Baseline, Weeks 1, 3, 6, 9, 12, and 16) prior to performing the lesion count. The IGA is intended for the global evaluation of papulopustular rosacea. Background nontransient erythema and telangiectasias should not be assessed as part of the IGA. The IGA score represents the subject’s condition at the time of the evaluation.

The following categories will be used from the IGA scale to perform the global evaluation of papulopustular rosacea:

Investigators Global Assessment (IGA) Scale

Grade	Grading Scale Score	Description of Papulopustular Rosacea Disease Status
Clear	0	No inflammatory papules or pustules.
Almost clear	1	Very few with 1 or 2 inflammatory papules/pustules.
Mild	2	Several (3-10) small inflammatory papules/pustules.
Moderate	3	11 to 19 small or large inflammatory papules/pustules and no nodules.
Severe	4	Numerous (≥ 20) small and or large inflammatory papules/pustules, and up to 2 nodules, (at baseline).

CONFIDENTIAL

Version Date: 10 July 2015

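### Both IGA tests adjust for center only and leave the baseline lesion count unused, forgoing a modest gain in power; the planned 95% is not reduced

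*Protocol*

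**What the plan says.** Protocol 7.7.10 gives one method for the 2-grade reduction and for Clear or Almost Clear: "Both IGA endpoints will be analyzed using a Cochran–Mantel–Haenszel (CMH) test, with center as the stratification factor". SAP 5.4.2 has the same sentence. Both documents add Fisher's exact test as corroboration when response is below 10%. Neither uses a baseline covariate for the IGA.

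Three other parts of the plan bear on this:

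- **Entry (protocol 7.2.1).** Inclusion criterion 6 requires "Subjects with a grade 4 (severe rosacea) on the 5-point Investigators Global Assessment (IGA) scale at Baseline". Criterion 3 requires at least 30 inflammatory lesions and sets no upper limit.
- **The scale (protocol 7.4.1).** Grades are bands of absolute lesion numbers: none; "Very few with 1 or 2 inflammatory papules/pustules" for grade 1; 3 to 10 for grade 2; 11 to 19 for grade 3; 20 or more for grade 4. Background erythema and telangiectasia are excluded.
- **Sample size (protocol 7.7.2, SAP 5.1).** For IGA 0/1 the plan assumes "17% of the subjects in the Omiganan treatment arm versus 6% in the vehicle arm" and concludes, with Fisher's exact test at 95% power, that "450 subjects (225 in each arm) are needed". The lesion endpoint needs only 86.

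Randomization includes site but not lesion count (protocol 7.7.3). SAP 5.4.2 and 7.0 record that enrollment was discontinued after the interim analysis and that all analyses are exploratory.

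**The concern.** Because everyone starts at grade 4, a 2-grade reduction means reaching 10 or fewer lesions, and Clear or Almost Clear means reaching 2 or fewer. The fall a subject needs is therefore set by the baseline count. From 30 lesions it is 20 for the first endpoint and 28 for the second; from 50 lesions it is 40 and 48. A variable that sets the distance to the threshold is likely to predict response. It is collected for every subject and already defined in SAP 6.1.

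A center-only CMH test ignores this information. It also leaves the estimate exposed to chance imbalance in baseline counts, which randomization by site does nothing to limit. With enrollment stopped early, the final sample is probably well below 450, and that is where both effects are largest. At stake is the precision of the IGA comparison, not its validity.

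**Working it through.** **1. The plan's own figure.** Inputs: 17% vs 6%, 225 per arm, and, from protocol 7.7.1, "all statistical tests will be two-sided with a significance level of 0.05". Exact power is the sum over x and y of Bin(x; 225, 0.17) × Bin(y; 225, 0.06), taken where the two-sided Fisher p-value is at most 0.05. The result is 95.1% (94.8% at 220 per arm), so the stated 450 reproduces. The calculation has no covariate, so omitting one takes nothing from it.

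**2. Could the count be prognostic?** Protocol 7.7.2 assumes that "subjects will have an average reduction of 13.5 inflammatory lesions, compared to 4 in the vehicle arm", with SD 12. Under a normal model with a fall that does not depend on baseline b, the omiganan chance of ending at k or fewer lesions is Phi((k − b + 13.5)/12).

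| Baseline b | 2 or fewer | 10 or fewer |
|---|---|---|
| 30 | Phi(−1.21) = 11.3% | Phi(−0.54) = 29.4% |
| 40 | Phi(−2.04) = 2.1% | Phi(−1.38) = 8.5% |
| 50 | Phi(−2.88) = 0.2% | Phi(−2.21) = 1.4% |

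This shows a direction only. The model gives at most 11.3% on omiganan and Phi((2 − 30 + 4)/12) = 2.3% on vehicle, both at the lowest permitted count. It cannot produce the assumed 17% and 6%.

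**3. Power at about the planned size.** Simulation used 28 pooled centers of 16 (448 subjects) and no missing data. Assumptions not in the documents: baseline count = 30 + gamma (shape 1.2, scale 12), and an odds ratio per SD of log count from 1.0 (no association) to 0.2.

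| Rates | Odds ratio per SD | CMH by center | Score test with log count |
|---|---|---|---|
| 17% vs 6% | 1.0 | 96.4% | 96.4% |
| 17% vs 6% | 0.5 | 96.5% | 97.0% |
| 17% vs 6% | 0.2 | 96.5% | 97.6% |
| 13% vs 6% | 0.5 | 73.0% | 73.6% |
| 13% vs 6% | 0.2 | 72.1% | 75.9% |

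The score test in this table is not stratified by center. Splitting each center at the median count inside the CMH test gave 95.2% to 96.6% at 17% vs 6%, mostly below center alone, because the strata become sparse.

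**4. Power at smaller sizes.** Assumptions: baseline count = 30 + exponential (mean 15); pools of about 20; no missing data. The response model was either additive (SD 12) or on the log scale (fall proportional to baseline), recalibrated to 17% vs 6% for IGA 0/1 and to an assumed 35% vs 20% for the 2-grade endpoint. Change in power for a center-stratified score test with log count, against CMH by center:

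- IGA 0/1, N = 120 to 200: about 0 to +4 points.
- 2-grade, N = 120 to 200: about +1 to +7 points.
- N of about 440: about 0 to +2 points.
- The low ends come from the log-scale model.
- Null rejection by the adjusted score test: 4.6% to 5.2%.

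**5. The form of the test matters.** In the same set-up, a Wald test of the conditional-logistic log odds ratio for IGA 0/1 at N = 120 lowered power from 48.8% (CMH) to 43.8% under the additive model, and from 46.0% to 37.3% on the log scale. The estimate diverged in about 2% to 3% of runs.

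**6. For scale.** Protocol 7.7.10 also allows an IGA claim when "either endpoint is significant at a two-sided 0.025 level". At 0.025 the exact Fisher power for IGA 0/1 is 91.5%, a drop of 95.1 − 91.5 = 3.6 points. That is more than the covariate could add at 448 subjects and the planned rates (97.6 − 96.5 = 1.1 points at most).

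**The case against.** CMH by center is a standard, valid test that matches the one stated randomization factor. Chance imbalance is not bias, and simulated null rejection for CMH was 4.1% to 5.1%. All analyses are now exploratory, so no confirmatory claim turns on this choice. The documents give no figure for how strongly baseline count predicts Week 12 IGA response. The Phase 2 strata in protocol 5.2 and SAP 1.0 concern how the treatment effect varies with count, which is a different matter. All of this stands and limits the point to efficiency.

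Four stronger readings are tempting and not supported:

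- **That lesion count is the only baseline severity measure that can vary.** Entry also admits IAE scores of 2 or more, any degree of telangiectasia and up to 2 nodules, and scaling and pruritus are graded. The count is only the main varying measure of what the IGA grades.
- **That planned power is lost.** The 450 was sized without a covariate, and its 95% holds.
- **That about 9 points are available on the endpoint that set the sample size.** One set of additive-model runs did show 45.5% to 54.5% (N = 120) and 67.1% to 76.5% (N = 200). Those are for the 2-grade endpoint at 35% vs 20%, rates found nowhere in the documents. The same runs gave IGA 0/1 gains of 2.8 and 2.7 points.
- **That the table in step 2 is the plan's prediction.** It conflicts with the plan's own response rates.

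**Conclusion.** The point holds as a missed efficiency. Both IGA tests leave out a covariate that is already collected and that the scale's definition makes a natural predictor. The stated 95% power at 450 is intact. The forgone gain is about 0 to 4 points for IGA 0/1 and about 1 to 7 points for the 2-grade endpoint at 120 to 200 subjects, and about 0 to 2 points at about 440. It is near zero if lesion falls are proportional to baseline.

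These ranges rest on assumed baseline distributions, assumed 2-grade rates and no missing data; the upper end for the 2-grade endpoint is the least certain. The final sample size is not stated. The interim was planned at about 60 completers per group, so the smaller sizes are the more relevant ones.

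**What to change.** In SAP 5.4.2, with protocol 7.7.10 aligned, analyze each IGA endpoint with a test stratified by pooled center, adjusted for log baseline inflammatory lesion count, and of score type. Either of two would do:

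- **A covariance-adjusted CMH.** Let U_y be the CMH numerator and U_z the same sum for log count, with stratified covariances V. Then Z = (U_y − (V_yz/V_zz) U_z) / sqrt(V_yy − V_yz²/V_zz).
- **The conditional-logistic score test** for treatment, stratified by pooled center, with log count in the model.

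Combine the signed Z scores (SE = 1) across the 100 imputations exactly as SAP 6.2 does for the CMH statistic. Report raw response rates by arm and keep the center-only CMH as supportive. Do not pool Wald log odds ratios for IGA 0/1: that loses power at small N and can diverge when responders are few. Do not add count as further CMH strata within centers.

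The cost is a short SAP change and a little code, with no new data. The downsides are small: the gain is negligible if the count is weakly prognostic, and any odds ratio shown is conditional on baseline count, so it should stand beside the raw rates.
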